10.3 Analyses Sets

All patients who are enrolled in the study and who receive at least one dose of VentaProst will be included in the intent-to-treat (ITT) analyses of pharmacodynamic and safety data. All available data will be used and missing data will not be estimated or carried forward in any statistical summary or analyses.

Descriptive summary statistics include the number of patients, mean, median, percent coefficient of variation (% CV) (if required), standard deviation, and minimum and maximum values (quantitative variables) or the number of patients and percentages by category (qualitative variables). Changes will be assessed as the difference between baseline measurements and the appropriate post-dose measurements unless otherwise

specified. Mean differences between active and historical control groups (when available) will be assessed and significance will be determined on the basis of a 95% CI. Individual patient listings of data will also be provided to allow for review of all pharmacodynamic, safety, and tolerability parameters.

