	Independent Safety Evaluation: Independent safety evaluation will be conducted by a licensed physician who is not involved in the VentaProst COVID-19 clinical study or the sponsoring organization.
Statistical Methods	All patients who are enrolled in the study and who receive at least one dose of study drug will be included in the intent-to-treat (ITT) analyses of pharmacodynamic and safety data. All available data will be used and missing data will not be estimated or carried forward in any statistical summary or analyses.
	Descriptive summary statistics include the number of patients, mean, median, percent coefficient of variation (% CV) (if required), standard deviation, and minimum and maximum values (quantitative variables) or the number of patients and percentages by category (qualitative variables). Changes will be assessed as the difference between baseline measurements and the appropriate post-dose measurements unless otherwise specified. Mean differences between active and historical control groups will be assessed and significance will be determined on the basis of a 95% CI.
	No formal estimate of the sample size has been made. This is an exploratory study and the number of patients was selected to enable an adequate clinical assessment of pharmacodynamic, safety, and tolerability parameters without presenting undue risk to a large number of patients.
Efficacy Analysis	Efficacy will be secondarily determined by summarizing success or failure to meet any of the primary or secondary endpoints as compared to Control treatment.
Safety Analyses	Safety data will be summarized for both treatment groups including frequencies and incidence rates. Safety will be assessed through monitoring of adverse events (AEs), serious adverse events (SAEs), chest CTs or chest X-rays, laboratory tests, oxygenation and ventilatory

parameters, and vital signs.

Table 2: Schedule of Assessments and Procedures

Screening VentaProst - Day 1					VentaProst Days 2-10							End of Study	
Study Procedures	Within 14 Days Prior to Baseline	Baseline 0 Hr	12 hrs	D-2	D-3	D-4	D-5	D-6	D-7	D-8	D-9	D-10/ End Study Treat ment	Day 28 (+/- 2 days)
Written Informed Consent ¹	X												
Demographics	X												
Medical History	X												
Review Inclusion/Exclusion Eligibility Criteria	X	X											
Medication History/ Prior Meds	X												
Physical Examination	X												
Weight/Height ²	X											X	
Randomization		X											
Chest CT Scan or CXR	X						X^3						

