Chemistry (including AST, ALT, AP, T. Bili) CBC, PT/PTT	X						X					X	
Pregnancy Test (Serum or Urine)	X												
COVID-19 diagnostic test such as molecular or antigen test	X												
Cardiac Troponin, and BNP	X						X					X	
Other blood tests: fibrinogen, ferritin, LDH, Triglycerides, D-Dimer, IL-6, ESR,CRP ⁴	X						X					X	
Administer VentaProst		X	X	X	X	X	X	X	X	X	X	X	
Vital Signs ⁵	X	X	X	X	X	X	X	X	X	X	X	X	
Oxygenation Measurements ⁶		X	X	X	X	X	X	X	X	X	X	X	
Ventilator Parameters ⁷		X	X	X	X	X	X	X	X	X	X	X	
AE/SAE Monitoring		X	X	X	X	X	X	X	X	X	X	X	X
Concomitant Medications		X	X	X	X	X	X	X	X	X	X	X	X
Prone position ⁸		X	X	X	X	X	X	X	X	X	X	X	

- ¹ Informed consent may be obtained after screening study procedures that were conducted as a part of the patient's standard of care.
- ² Height only performed at screening
- ³ Chest CT or CXR may be performed anywhere from 3-8 days as clinically warranted.
- ⁴ These tests are collected only if available as Standard of Care
- ⁵ Vital signs: Prior to initiating VentaProst, Days 1-10 twice daily (morning and evening) at the same time to reduce exposure to Health Care Professionals to include; temperature, pulse rate, blood pressure.
- ⁶Continuous SpO2 via pulse oximetry
- Ventilator Parameters will be collected twice daily along with vital signs and include: Ventilator Type, Ventilator Mode, FiO₂, Inspiratory Time, Mean Airway Pressure, Peak Inspiratory Pressure, Positive End Expiratory Pressure, Tidal Volume and Respiratory Rate
- ⁸Time Prone Position 16 hours per day per OSU protocol

TABLE OF CONTENTS

INV	ESTIG.	ATOR'S SIGNATURE PAGE	3
1.	CLIN	IICAL PROTOCOL SYNOPSIS	4
TAE	BLE O	F CONTENTS	11
		ACRONYMS, ABBREVIATIONS AND	
		ION OF TERMS	14
2.	BACI	KGROUND AND RATIONALE	17
	2.1	Introduction	
	2.2	VentaProst	

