9.1.2.4 Days 2-10 (While on study drug)

- Continue to administer study drug if clinically indicated.
- Adverse Event/SAE assessment daily
- Concomitant medication evaluation daily
- Oxygenation measurement via continuous pulse oximetry (SpO₂)
- Ventilatory parameters assessed twice daily: Ventilator Type, Vent Mode, FiO₂, Inspiratory time, Mean Airway Pressure, Peak Inspiratory Pressure, Positive End Expiratory Pressure, Tidal Volume, and Respiratory Rate
- Vital signs will be assessed twice daily in AM and PM. Efforts will be made to obtain vital signs at the same time each day. Vital signs include: temperature, pulse rate, and blood pressure.
- Time Prone Position-16 hours per day per OSU Protocol

- Chest X-ray (Days 3-8 as clinically indicated)
- Full Chemistry Panel including LFTs, CBC with Diff including neutrophils and lymphocytes, PT/PTT, troponin, and BNP(Days 5 & 10).
- Triglycerides, LDH, ferritin, fibrinogen, CRP, ESR, IL 6 and D-Dimer may be collected if the subject's condition warrants it at Days 5 and Day 10.
- Obtain weight. (Day 10 only or at end of study drug dosing)

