10.3 Analyses Sets

All patients who are enrolled in the study and who receive at least one dose of study drug will be included in the intent-to-treat (ITT) analyses of pharmacodynamic and safety data. All available data will be used and missing data will not be estimated or carried forward in any statistical summary or analyses.

Descriptive summary statistics include the number of patients, mean, median, percent coefficient of variation (% CV) (if required), standard deviation, and minimum and maximum values (quantitative variables) or the number of patients and percentages by category (qualitative variables). Changes will be assessed as the difference between baseline measurements and the appropriate post-dose measurements unless otherwise specified. Mean differences between active and control groups (when available) will be assessed and significance will be determined on the basis of a 95% CI. Individual patient listings of data will also be provided to allow for review of all pharmacodynamic, safety, and tolerability parameters.

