10.6.2 Secondary Efficacy Endpoints

Key secondary endpoints include:

- 1. Improvement in oxygenation defined as any one of the following:
 - Stabilization of PaO2/FIO2 >250
 - Improvement in FIO2 by 50% or improvements ≥15% in S/F, P/F ratio from baseline at 12 hours, Day 5 and Day 10 (or end of treatment)
- 2. Improved clinical outcomes defined as one of more of the following:
 - Time to extubation following the site's extubation protocol
 - Free from reintubation
 - Reduction in ICU days
 - Reduction in the number of re-admissions to the ICU due to COVID-19 within 28 days
 - Reduction in total hospital days
 - Mortality [28 days] defined as Cardiopulmonary mortality from all causes
- 3. Safety
 - Monitoring of adverse events (AEs), serious adverse events (SAEs), chest CT or Chest X-rays, vital signs, ventilatory/oxygenation parameters, and laboratory tests.

10.6.3 Key Exploratory Endpoints include:

- Change in LDH
- Change in fibrinogen
- Change in WBC count including lymphocytes and neutrophil subsets
- Change in triglycerides
- Change in ferritin
- Change in CRP / ESR
- Change in IL-6
- Change in D-Dimer

Changes in these parameters will be assessed for each patient from baseline to end of study as well as changes between the active and control groups.

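### The current synopsis still names historical controls as the comparator of a randomised, concurrently controlled trial and must be brought into line with section 10.3; baseline adjustment is a cheap addition where continuous changes are compared

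*Combined protocol and SAP*

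**What the plan says.** The combined document holds four protocol versions. The last, with weaning steps of 6.8 ng/kg/min in its synopsis, is the current one.

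- **Synopsis, Statistical Methods (current):** "Mean differences between active and historical control groups will be assessed and significance will be determined on the basis of a 95% CI".
- **Section 10.3 (current):** "Mean differences between active and control groups (when available) will be assessed and significance will be determined on the basis of a 95% CI".
- **Section 10.3 (superseded open-label version):** "Mean differences between active and historical control groups (when available) will be assessed". That design had 10 treated patients and 20 matched historical controls.
- **Use of baseline, section 10.3:** "Changes will be assessed as the difference between baseline measurements and the appropriate post-dose measurements unless otherwise specified". No covariate or model is named.
- **Exploratory markers, section 10.6.3:** changes are assessed within patients "as well as changes between the active and control groups". The list includes "Change in WBC count including lymphocytes and neutrophil subsets".
- **Data schedule:** the Table 2 row "Chemistry (including AST, ALT, AP, T. Bili) CBC, PT/PTT" is marked for Screening, Day 5 and Day 10, as is the troponin and BNP row. Section 9.1.2.4 agrees: "CBC with Diff including neutrophils and lymphocytes, PT/PTT, troponin, and BNP(Days 5 & 10". LDH, fibrinogen, ferritin, triglycerides, CRP/ESR, IL-6 and D-dimer are collected only when standard of care provides them (Table 2, footnote 4).
- **Section 10.1:** no SAP will be developed, because the trial is exploratory.

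**The concern.** With no SAP to follow, the protocol text is the only analysis rule, and it names two different comparators. Taken literally, the synopsis sets the randomised Control arm aside and compares Active with patients whom the current version never defines. That would give up the protection of randomisation. Anyone who works from the synopsis alone has the wrong rule in hand.

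There is also a smaller missed opportunity. Some outcomes are compared as changes between two arms of 10, baseline values are already scheduled, and yet baseline enters only through subtraction. Adjusting for it usually gives a narrower interval at no data cost.

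**Working it through.** **1. Comparator statements in the current version, side by side**

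| Place | Comparator |
|---|---|
| Synopsis, Statistical Methods | historical control groups |
| Synopsis, Efficacy Analysis | Control treatment |
| Section 3.3, Study Design | concurrent saline Control, 10 v 10, double-blind |
| Section 4 | two randomised arms, about 20 patients; no historical cohort |
| Section 10.3 | control groups |
| Section 10.4 | randomised 1:1 |

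One entry disagrees with the rest. Its source is visible: the same sentence stands in the open-label synopsis and in the open-label section 10.3, where it fitted the design. When the design changed, section 10.3 was corrected and the synopsis was not.

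**2. What baseline adjustment would give**

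The plan states no SD, correlation or power, so it has no figure to reproduce. The inputs are n observed per arm (10 planned, sections 3.3 and 4), the baseline to follow-up correlation r, and k, the follow-up SD divided by the baseline SD. Both r and k are assumptions.

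With the baseline SD set to 1, each estimator has, per patient:

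- change score: variance 1 + k² − 2rk, with 2n − 2 degrees of freedom;
- ANCOVA: variance k²(1 − r²) × [1 + 1/(2n − 4)], with 2n − 3 degrees of freedom. The bracket is the price of estimating the slope.

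Approximate width ratio (ANCOVA / change) = √{k²(1 − r²)[1 + 1/(2n − 4)] / (1 + k² − 2rk)} × t(2n − 3)/t(2n − 2).

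Example with n = 10, r = 0.5, k = 1: 0.75 × 1.0625 / 1 = 0.797; √0.797 = 0.893; × 2.110/2.101 = 0.896. Simulation of two-arm trials with normal data gives 0.895.

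Simulated change in 95% CI width, ANCOVA against change score, 10 per arm (minus = narrower):

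| k | r = 0.3 | 0.5 | 0.7 | 0.8 | 0.9 |
|---|---|---|---|---|---|
| 0.8 | −26.7% | −21.9% | −18.1% | −17.3% | −19.3% |
| 1 | −16.6% | −10.5% | −4.8% | −2.0% | +0.7% |
| 1.25 | −8.5% | −2.3% | +2.3% | +3.3% | +0.7% |
| 1.5 | −3.5% | +1.5% | +3.2% | +0.9% | −8.9% |

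Type I error was 4.9% to 5.1% for both methods in every cell.

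**3. Fewer patients observed**

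The loss is greatest when r × k = 1, because the true slope is then 1 and the change score is already the best adjustment. At r = 0.8, k = 1.25, simulation gives:

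| Observed per arm | ANCOVA interval wider by |
|---|---|
| 10 | 3.3% |
| 8 | 4.5% |
| 6 | 7.0% |
| 5 | 9.7% |
| 4 | 15% |

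This matters here. Section 9.1.2.4 schedules the later samples while patients are on study drug, and section 10.3 allows no imputation, so Day 5 and Day 10 may have well under 10 per arm.

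**The case against.** **The comparator error is one word.** Section 10.3 and the Efficacy Analysis row are right, and with no historical cohort defined, a historical comparison could not be run from the current protocol. This stands as to intent. A reader might infer that a historical comparison is planned; the body text does not support that. It remains true that the only analysis rule contradicts itself and that no later document is due to settle it.

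**ANCOVA is a preference.** Both methods hold the error rate, section 10.3 leaves room for other specifications, and ANCOVA is wider in 7 of the 20 cells above. This largely stands. The case for ANCOVA is an uneven trade (gains up to about 27%, losses up to about 3% at 10 per arm), and that trade worsens as patients leave. A reader might take 3% as a general ceiling on the loss; it holds only with 10 observed per arm.

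**It reaches few endpoints.** This stands. The primary endpoint (section 10.6.1) is binary failure, and secondary oxygenation (section 10.6.2) is a responder definition. S/F, FiO2, troponin and BNP enter only as threshold criteria. Of the named change endpoints, only WBC and its subsets are measured in all patients by schedule. ICU days, hospital days and time to extubation have no baseline value.

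**'When available' may be deliberate.** In section 10.3 it could be read as a second leftover, as if the randomised Control arm might be unavailable. But the current version collects seven exploratory items only as standard of care, so the phrase has a live meaning there.

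**'Significance' is tied to no endpoint or time point.** True, but in a trial that calls itself exploratory and has no formal sample size this is a matter of labelling. It should not be read as a failed confirmatory error-control plan.

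**Conclusion.** The comparator contradiction is certain and should be corrected. It rests on the text alone and needs no assumption. Its practical size is small if the body text is followed, as the rest of the protocol indicates it will be. It would be serious only if the synopsis were applied literally.

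Baseline adjustment is a modest optional gain in precision and corrects no bias. With equal SDs and 10 observed per arm, the interval is about 17%, 10%, 5% and 2% narrower at r = 0.3, 0.5, 0.7 and 0.8. These figures assume normal data and values of r and k that the documents do not give. At some values the sign reverses, by about 3% at worst with 10 per arm, 7% with 6 and 15% with 4.

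**What to change.** 1. Delete 'historical' from the Statistical Methods row of the current synopsis, so that the comparator is the concurrent randomised Control arm throughout.
2. In section 10.3, limit 'when available' to data collected only as standard of care.
3. Where continuous changes are compared between arms, estimate the difference by ANCOVA with the baseline value as covariate and give the number observed per arm. This covers WBC, lymphocyte and neutrophil counts, and S/F, FiO2, troponin or BNP if they are summarised as continuous values. Use it only at visits where most patients are observed, for example at least 8 per arm. Leave the binary primary endpoint and the responder-type secondary endpoints as counts per arm, which sections 10.3 and the Efficacy Analysis row already provide for.
4. Optional: report the 95% CIs as estimates without significance statements, in keeping with the exploratory label.

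Cost: protocol wording and standard software, with no new data, visits or patients. ANCOVA spends one degree of freedom and carries the possible loss shown above. If troponin or BNP were analysed on a log scale, a rule for values below the detection limit would be needed.

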ng	Nanogram
OR	Operating Room
OTC	Over-the-Counter
PAH	Pulmonary Arterial Hypertension
PaO ₂	Partial Pressure of Oxygen in Arterial Blood
PAP	Pulmonary Arterial Pressure (mm Hg)
PCWP	Pulmonary Capillary Wedge Pressure
PD	Pharmacodynamic
PEEP	Positive End Expiratory Pressure
PH	Pulmonary Hypertension
PIP	Peak Inspiratory Pressure
PK	Pharmacokinetic
PP	Per Protocol
	ı

Abbreviation	Term
PGI ₂	Prostaglandin I ₂ (epoprostenol)
PVR	Pulmonary Vascular Resistance (dyn/sec/cm ⁵)
RBC	Red Blood Cell (count)
RH	Right Heart
RHF	Right Heart Failure
RT-PCR	Reverse Transcription Polymerase Chain Reaction
RVSWI	Right Ventricular Stroke Work Index
SAE	Serious Adverse Event
SaO ₂	Arterial Oxygen Saturation
sPAP	Systolic Pulmonary Arterial Pressure (mm Hg)
sSAP	Systolic Systemic Arterial Pressure (mm Hg)
SE	Standard Error
SOP	Standard Operating Procedures
SOC	Standard of Care
SpO_2	Oxygen Saturation by Pulse Oximetry
Study Drug	Active or Control Treatment
SVR	Systemic Vascular Resistance
TEAE	Treatment-Emergent Adverse Event
TEE	Transesophageal Echocardiogram
TPG	Transpulmonary Gradient
t _{1/2}	Half-Life
TLD	Total Lung Dose
ULN	Upper Limit of Normal
VA-ECMO	Veno-arterial Extracorporeal Membrane Oxygenation
VentaProst	VentaProst TM – Drug/device combination product consisting of aerosolized epoprostenol delivered via dedicated drug delivery system
VentaProst Nebulizer	The nebulizer assembly that is part of the VentaProst delivery system
VTE	Venous Thromboemobolism
VV ECMO	Venovenous Extracorporeal Membrane Oxygenation
WBC	White Blood Cell (count)
WHO	World Health Organization

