6. CRITERIA FOR EVALUATION

6.1 Primary Endpoint

- 1. Reduction of respiratory failure. Failure is defined by any one of the following:
 - Requires VV ECMO
 - Inability to extubate within 10 days or reintubation within < 24 hours
 - Change in S/F, oxygenation index and P/F ratio (≥15%) from baseline to 12 hours, Days 1, 2, 3, 4, 5, 6, 7, 8, 9 and Day 10 (or end of treatment)

or

- 2. Reduction of cardiac or circulatory failure. Failure is defined by any one of the following:
 - Need to begin inotropic therapy or 10% increase in current vasopressor therapy
 - Worsening hemodynamic parameters
 - Cardiac troponin >20% from baseline
 - BNP > 15% of baseline
 - Need for temporary mechanical circulatory support (IABP, Impella)
 - Requires VA ECMO

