6.2 Secondary Endpoints

- 1. Improvement in oxygenation defined as any one of the following:
 - Stabilization of PaO2/FIO2 >250
 - Improvement in FIO2 by 50% or improvements ≥15% in S/F, P/F ratio from baseline at 12 hours, Day 5 and Day 10 (or end of treatment)
- 2. Improved clinical outcomes defined as one of more of the following:
 - Time to extubation following the site's extubation protocol

- Free from re-intubation
- Reduction in ICU days
- Reduction in the number of re-admissions to the ICU due to COVID-19 within 28 days
- Reduction in total hospital days
- Mortality [28 days] defined as Cardiopulmonary mortality from all causes

3. Safety and tolerability

 Monitoring of adverse events (AEs), serious adverse events (SAEs), chest CT or Chest X-rays, vital signs, ventilatory/oxygenation parameters, and laboratory tests.

6.3 Exploratory endpoints will include (where available as part of standard of care):

- Change in LDH
- Change in fibrinogen
- Change in WBC count including lymphocytes and neutrophil subsets
- Change in triglycerides
- Change in ferritin
- Change in CRP / ESR
- Change in IL-6
- Change in D-Dimer

Changes in these parameters will be assessed for each patient from baseline to end of study as well as changes between the active and control groups.

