7.1.3 Laboratory Measurements

Clinical laboratory measurements to b	e performed are listed below. The Schedule of Assessments			
and Procedures shows the time points a	t which blood will be collected for clinical laboratory tests and			
pregnancy testing. The Baseline for laboratory tests is the Screening assessment.				
Category	Parameters			
	H 11: 1 / PDC WDC '4 1'CC / 1			

Category	Parameters	
Hematology-CBC with diff	Hemoglobin, hematocrit, RBC, WBC with differential (neutrophils, lymphocytes, monocytes, eosinophils, basophils), platelets	
Full Chemistry Panel		
Electrolytes	Sodium, potassium, chloride, bicarbonate, calcium	
Liver function tests	AST, ALT, AP, total bilirubin	
Renal function parameters	BUN, creatinine	
Coagulation Studies	PT/PTT	
Other	Serum or urine pregnancy test, COVID-19 diagnostic test, Troponin, and BNP (fibrinogen, ferritin, LDH, Triglycerides, D-Dimer, IL-6, ESR,CRP may be obtained if the patient's standard of care warrants the tests)	

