9.1.2.3 Day 1-12 hours

- Continue to administer study drug if clinically indicated.
- Adverse Event/SAE assessment daily
- Concomitant medication evaluation daily
- Oxygenation measurement via continuous pulse oximetry (SpO₂)
- Ventilatory parameters assessed twice daily while on study drug: Ventilator Type, Vent Mode, FiO₂, Inspiratory time, Mean Airway Pressure, Peak Inspiratory Pressure, Positive End Expiratory Pressure, Tidal Volume, and Respiratory Rate
- Vital signs will be assessed twice daily in AM and PM. Efforts will be made to obtain vital signs at the same time each day. Vital signs include: temperature, pulse rate, and blood pressure.
- Time Prone Position-16 hours per day per OSU Protocol

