10.6 Criteria for Evaluation

10.6.1 Primary Efficacy Endpoint

The primary efficacy endpoint:

- 1. Reduction of respiratory failure. Failure is defined by any one of the following:
 - Requires VV ECMO
 - Inability to extubate patient within 10 days or reintubation within <24 hours
 - Change in S/F, oxygenation index and P/F ratio (\geq 15%) from baseline to 12 hours, Days 1, 2, 3, 4, 5, 6, 7, 8, 9 and Day 10 (or end of treatment)

or

- 2. Reduction of cardiac or circulatory failure. Failure is defined by any one of the following:
 - Need to begin inotropic therapy or 10% increase in current vasopressor therapy

- Worsening hemodynamic parameters
- Cardiac troponin >20 % from baseline
- BNP \geq 15% of baseline
- Need for temporary mechanical circulatory support (IABP, Impella)
- Requires VA ECMO

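### The current protocol schedules no arterial PaO2 for its P/F and PaO2/FiO2 endpoint items, and allows a troponin or BNP baseline taken before intubation

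*Combined protocol and SAP*

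**What the plan says.** All references are to the last of the protocol versions in the combined document, the one with enrolment within 48 hours of ventilation.

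**Oxygenation.** Section 6.1 counts as respiratory failure "Change in S/F, oxygenation index and P/F ratio (≥15%) from baseline to 12 hours" and then on each day to Day 10 or end of treatment. Section 10.6.1 repeats "oxygenation index and P/F ratio". Section 6.2 adds the secondary criterion "Stabilization of PaO2/FIO2 >250". Footnote 6 to Table 2 defines the oxygenation row as "⁶Continuous SpO2 via pulse oximetry", and Section 9.1.2.3 likewise lists "Oxygenation measurement via continuous pulse oximetry". The ventilator list includes FiO2 and mean airway pressure.

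**Troponin and BNP.** Section 6.1 lists "Cardiac troponin >20% from baseline" and a BNP threshold among six cardiac or circulatory criteria, any one of which is failure. Section 7.1.3 states: "The Baseline for laboratory tests is the Screening assessment". Table 2 and Section 9.1.1 put Screening within 14 days before Baseline. Table 2 footnote 1 and Sections 3.3 and 9.1.1 let procedures done before consent as standard of care serve as Screening. Section 4.1 requires enrolment within 48 hours of ventilation. The later draws are on Days 5 and 10.

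**Missing data.** Section 10.3 uses all available data and neither estimates missing values nor carries any forward. Section 10.1 says that no statistical analysis plan will be written.

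**The concern.** P/F and PaO2/FiO2 cannot be calculated without an arterial PaO2, and the usual form of the oxygenation index needs one too. If the plan does not require or time that measurement, the values will come from gases drawn for clinical reasons. With no selection rule, the choice of gas is left to whoever scores the endpoint. A patient with no gas before first dose cannot be scored on P/F change at any time. With no separate analysis plan, no later document is due to supply the rule.

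For troponin and BNP, the score is meant to capture change during the study. A baseline drawn before intubation also captures the deterioration that led to intubation. The study drug could not have caused or prevented that change, but it can still be counted as on-study failure.

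**Working it through.** The plan states no figure on this point, so there is none to reproduce. The check sets what the endpoints need against what is scheduled, and then does simple date arithmetic.

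**1. Inputs for each oxygenation item** (Table 2; Sections 6.1, 6.2, 7.1.3, 9.1.1 and 9.1.2.2 to 9.1.2.4)

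| Item | Needs | Scorable from scheduled data? |
|---|---|---|
| S/F | SpO2, FiO2 | Yes |
| FiO2 improvement by 50% | FiO2 | Yes |
| P/F | PaO2, FiO2 | No, PaO2 is not scheduled |
| Oxygenation index (usual form; not defined in the plan) | mean airway pressure, FiO2, PaO2 | No, PaO2 is not scheduled |
| PaO2/FiO2 above 250 | PaO2, FiO2 | No, PaO2 is not scheduled |

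So 2 of the 3 indices in the primary oxygenation item lack a scheduled input.

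**2. P/F values per patient.** Baseline (1) + 12 hours (1) + Days 1 to 10 (10) = 12. If Day 1 is the 12-hour reading, the total is 11. Scheduled PaO2 values: 0.

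**3. Age of the troponin or BNP baseline**
- The oldest Screening result is 14 days before Baseline.
- Randomization is at Baseline and within 48 hours of ventilation, so intubation is 0 to 2 days before Baseline.
- Longest lead over intubation: 14 − 2 = 12 days, up to 14 − 0 = 14 days.
- A sample taken specifically for the study follows consent (Section 11.1.3). Section 3.3 puts consent within 48 hours of ventilation, so that sample follows intubation. The problem therefore arises only with reused standard-of-care results.
- Share of cardiac criteria affected: 2 of 6.

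**4. Data after an early drug stop.** Section 5.4.2 and Sections 9.1.2.2 to 9.1.2.4 limit ventilator data to time on study drug. Section 7.1.1 and Table 2 footnote 5 set vital signs at Days 1 to 10, and footnote 7 collects ventilator values along with them. However, Section 9.1.2.2 also limits vital signs to time on study drug. For SpO2, only the heading of Section 9.1.2.4 sets such a limit. The daily marks in Table 2 do not settle the matter, because the row for administering the drug has the same marks through Day 10.

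**The case against.** The strongest reply is that ventilated patients in an ICU have blood gases taken anyway. Section 10.3 uses all available data, and Section 11.2.3 counts hospital charts and laboratory results as source documents, so these gases may be used. That stands, and it means that none scheduled must not be read as none measured. A reader might infer that P/F will be missing throughout; the documents give no basis for any estimate of missingness. What remains is the absence of a rule. Where this protocol relies on routine-care results for other tests, such as LDH and IL-6, it says so (Table 2 footnote 4, Sections 6.3 and 7.1.3). It says nothing of the kind for PaO2.

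On troponin and BNP, a reader might compute that with a 14-day-old baseline, 14 of the 14 + 4 = 18 days to the Day 5 draw (78%), or 14 of the 14 + 9 = 23 days to the Day 10 draw (61%), fall before first dose. The arithmetic is right, but these are shares of elapsed time at the limit of the window. They are not rates of misclassified failure, and the documents do not say how often old results would be reused. Baseline date is also not the only difficulty with BNP. Its threshold is worded as a percentage of baseline rather than a rise above it, and the change proposed here does not repair that.

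On data after an early stop, a reader might infer an outright contradiction for all oxygenation data. The text does not support that. It is an ambiguity, mainly about ventilator values, and the column heading and the end-of-treatment wording can be read as on-drug collection only.

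**Conclusion.** The first two parts hold and are worth correcting. None of the 12 (or 11) P/F values per patient, and no value for the PaO2/FiO2 criterion, has a scheduled PaO2 or a rule for choosing a routine one. S/F and the FiO2 criterion are unaffected. The primary item also leaves open whether all three indices must change or any one suffices, and which direction is failure. The first of these decides whether a missing gas blocks the whole item or only part of it.

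A permitted troponin or BNP baseline can precede intubation by up to 12 to 14 days, so change before randomization can be scored as failure on 2 of 6 cardiac criteria. This is something the rules allow; some patients will have a Screening sample taken after intubation. Because patients are randomized, it should occur about equally in both arms and mainly dilute a difference, not favour one arm.

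The third part is a minor wording query. A patient still ventilated at Day 10 generally already fails on extubation, so it matters mostly for patients who stop drug early and are extubated by then.

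These conclusions rest on the scheduled assessments, the stated time windows and the usual form of the oxygenation index. No event rates are assumed.

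**What to change.** 1. **Gases.** Keep the endpoints. State that P/F, PaO2/FiO2 and the oxygenation index use routine-care arterial gases with the paired FiO2. Take the last gas before first dose as baseline. Take one gas per named time point by a fixed rule with a window: for example, nearest to 12 hours within a stated window, and for Days 2 to 10 the gas nearest to the morning ventilator reading on that calendar day. A rule based only on closeness to the scheduled time would not work for Days 2 to 10, which have no clock time. Define the oxygenation index, say whether Day 1 is the 12-hour reading, say whether all or any of the three indices must change and in which direction, and report S/F alongside.
2. **Troponin and BNP.** Replace the Screening baseline with the last available value before first dose, taken after intubation where one exists. Flag patients whose baseline predates intubation.
3. **Wording.** Reconcile Sections 5.4.2 and 9.1.2.2 to 9.1.2.4 with Section 7.1.1 and Table 2 footnotes 5 and 7. State whether endpoint data run to Day 10 after an early drug stop.

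The cost is protocol and data-form wording, ethics approval where Section 11.2.1 requires it, and modest chart abstraction for about 20 patients at one site. No draw or procedure is added. Some time points will still have no gas, and a few pre-intubation baselines will remain.
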